reflex^{21,22}, increases corticospinal excitability²⁴, and increases motor unit recruitment.⁴¹ We propose to deliver tsDCS using an electrode montage that targets lumbar spinal excitability, and has been validated by modeling of electrical current flow⁴² and by gains in lower extremity motor performance.²⁵ The objective with tsDCS is to bring spinal neurons closer to their discharge threshold. When applied during walking, this increased excitability of spinal neurons contributes to a physiological environment that is more responsive to task-specific activation by descending/motor and afferent/sensory pathways.²² The proposed study is designed to provide evidence of short term effects of tsDCS on task practice, which can be translated to longer rehabilitation interventions in the future.

5. Specific Aims:

Specific Aim 1: Acquire preliminary data to assess whether active tsDCS and/or textured shoe insoles improve practice-related gains in performance and retention for a complex obstacle walking task.

Hypothesis 1a: Within-session, effect sizes will support the following group differences for improved walking speed and reduced prefrontal activity after the practice period:
[active/textured] > [active/smooth = sham/textured] > [sham/smooth]

Hypothesis 1b: At the 2-day retention test, effect sizes will support the same findings described for Hyp 1a.

Specific Aim 2: Establish evidence of increased spinal excitability following tsDCS.

Hypothesis 2: Spinal excitability post-stimulation (measured by H-reflex) will be significantly elevated above pre-stimulation baseline for active tsDCS but not sham tsDCS.

6. Research Plan:

Study Overview

All study procedures will be conducted at the Brain Rehabilitation Research Center within the Malcom Randall VA Medical Center. Up to forty older men and women will be enrolled in the intervention component of this study. A larger number will be enrolled for onsite screening, because some will fail the screening tests and not proceed to the study intervention.

Participants will undergo the following sequence of events:

- *Telephone Screening:* Volunteers will be screened by telephone to determine if they meet basic enrollment criteria including age and general health status.

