- *Informed Consent and Onsite Screening Visit:* Volunteers who pass the phone screen will be invited to participate in on-site screening. Informed consent will be obtained. Mobility function, cognitive screening, and somatosensory screening will be conducted. This visit will last approximately 3 hours.
- *Study Intervention Visit(s):* Qualifying participants will be invited to participate in the full study. They will attend either one or two intervention sessions (randomly determined to study dosage effects) in which they will practice a “locomotor learning” task comprised of a 10m walking course with obstacles and transitions between hard and soft floor surfaces. During this task they will receive either active or sham transcutaneous spinal direct current stimulation. They will also wear either smooth or textured shoe insoles. Biomechanical and neural control of walking will be assessed with various non-invasive

modalities. Participants will also undergo H-reflex assessment. This visit will last approximately 3 hours.

- *Follow up Visit:* 2 days following the study intervention visit, participants will return to perform the “locomotor learning” task again so that we can assess retention of learning. This visit will last approximately 2 hours.

Telephone Screening

Participants will be screened by telephone to determine if they meet the following criteria:

Inclusion criteria

- Age 65 years or older
- Willingness to be randomized to either intervention and to participate in all aspects of study assessment and intervention

Exclusion criteria

- Diagnosed neurological disorder or injury of the central nervous system, or observation of symptoms consistent with such a condition (spinal cord injury, Alzheimer’s, Parkinson’s, stroke, etc.)
- Contraindications to non-invasive spinal stimulation including any prior spinal surgical procedure
- Chronic lower back pain
- Obesity, defined as Body Mass Index exceeding 30. This is due to the potential influence of body fat on the amplitude of electrical current flow to the spinal cord.
- Use of medications affecting the central nervous system including, but not limited to, benzodiazepines, anti-cholinergic medication and GABAergic medication.
- severe arthritis, such as awaiting joint replacement
- current cardiovascular, lung or renal disease; diabetes; terminal illness
- myocardial infarction or major heart surgery in the previous year

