- Cognitive Assessment Battery from Cambridge Brain Sciences, which includes up to 12 cognitive tests. All are short, simple, computer-based assessment that assess domains of cognitive such as spatial working memory, response inhibition, and reasoning. A specific example is the visuospatial working memory test, in which participants are asked to remember the sequence and location of shapes that appear and disappear from the screen.

Following the screening visit, study staff will evaluate performance/responses relative to the study enrollment inclusion/exclusion criteria. Medical records may be examined to verify absence of exclusion diagnoses, and to obtain complete/accurate medication lists. Individuals who meet all criteria will be invited to enroll in the full study.

At the discretion of the Principal Investigator, any individual may be deemed ineligible for further participation in this study if there are concerns about the individual's capability to perform study procedures or if it may be unsafe for the volunteer to participate in the study. Furthermore, minor exceptions to the inclusion/exclusion criteria may be permitted at the discretion of the Principal Investigator if those exceptions do not influence participant safety. For example, small deviations from the target range of walking speed or somatosensory function. This is important to ensure that individuals are not excluded for insignificant reasons and to facilitate meeting enrollment benchmarks.

Walking Practice Visit(s)

Walking practice protocol

Walking practice will consist of 10-20 passes over a 10-meter complex walking course consisting of foam obstacles of various heights and widths, as well as transitioning between hard (bare floor) and soft surfaces (exercise mats). Each pass will be separated by a short rest period of approximately one minute. Participants will be instructed to walk as fast as safely possible.

For most participants, the walking practice protocol will be completed in a single visit. However, a subset of participants (up to 20) will perform the walking practice protocol twice so that we can study dosage effects (i.e., one session versus two sessions). This subset will be selected randomly.

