Participants may be asked to wear sensors on their fingers that measure skin conductivity, which is a measure of sympathetic nervous system arousal. Adhesive electrodes are placed on the index and ring fingers. We will use a commercially available data acquisition unit (Flexcomp Infiniti by Thought Technologies Inc).

Video, photos, and voice recordings

During this study, videos and/or photos may be taken during to document the functional abilities of participants, and for possible use in research presentations or education. We may also use voice recordings to capture performance on cognitive assessments such as verbal fluency or serial-7 subtraction tests. At the time of consent, participants will choose what their videos/photos/recordings can be used for. We will avoid capturing images of the participants' faces, and will obscure or delete any such images.

Follow Up Visit

Approximately 2 days after the intervention visit, participants will return to the lab and perform several more walking trials on the same course that was used for practice, so that we can evaluate retention of walking performance.

The dual-task walking assessment will also be repeated.

Possible Discomforts and Risks:

As with all physical activity, there is a risk of falling while we test or train walking ability. Falls can lead to injuries ranging from minor to serious. When participants are asked to walk on a treadmill (e.g., during the H-reflex test described above), they will wear a safety harness so that they cannot fall off the treadmill. The harness will catch the participant, but might still cause injury (scrapes or bruises) if there is forceful contact with the straps. It is also possible that participants could experience musculoskeletal injury such as an ankle sprain. It is possible that the participant may experience fatigue, soreness, and discomfort due to physical activity associated with this study. These are unlikely to be worse than what he/she would experience due to increased physical activity outside of our study. These are normal responses to exercise and most discomfort would generally disappear within a matter of days. In general, walking exercise is strongly recommended for all adults, including elderly adults with medical conditions.

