
fNIRS Safety: fNIRS poses no safety risk. Infrared light from the fNIRS device is not harmful and elicits no sensation. Sensors may be secured to the skin using adhesive tape, which could lead to mild skin irritation in those who are sensitive to adhesives. If a person indicates or displays such a sensitivity, we will avoid using adhesive tape and instead use elastic fabric or straps to secure the sensors.

Questionnaire administration: Questionnaire data are collected in secure spaces where the interview cannot be overheard. Participants will be informed that they are not required to answer questions that they do not wish to answer.

Statistical Analysis Plan: Effect sizes for between-group differences will be calculated for *improved* walking speed after the practice period. For Hypothesis 1b, an analogous comparison

will be made for the 2-day retention test. We do not claim that this study is powered to conduct statistically significant tests of group differences, although we will examine our data for evidence of directional effects:

[active/textured] > [active/smooth = sham/textured] > [sham/smooth].

Rather, our goal is to calculate effect sizes and variance of response in order to provide data needed for powering a future full scale trial. This study will also provide information on the feasibility of our protocol including safety and recruitment.

1. Fielding, R.A., W.J. Rejeski, S. Blair, T. Church, M.A. Espeland, T.M. Gill, J.M. Guralnik, F.C. Hsu, J. Katula, A.C. King, S.B. Kritchevsky, M.M. McDermott, M.E. Miller, S. Nayfield, A.B. Newman, J.D. Williamson, D. Bonds, S. Romashkan, E. Hadley, M. Pahor, and L.R. Group, *The Lifestyle Interventions and Independence for Elders Study: design and methods*. Journals of Gerontology. Series A, Biological Sciences and Medical Sciences, 2011. **66**(11): p. 1226-37.
2. Shumway-Cook, A., A. Patla, A. Stewart, L. Ferrucci, M.A. Ciol, and J.M. Guralnik, *Environmental components of mobility disability in community-living older persons*. J Am Geriatr Soc, 2003. **51**(3): p. 393-8.
3. Shumway-Cook, A., A.E. Patla, A. Stewart, L. Ferrucci, M.A. Ciol, and J.M. Guralnik, *Environmental demands associated with community mobility in older adults with and without mobility disabilities*. Phys Ther, 2002. **82**(7): p. 670-81.

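### A second practice session is randomised to study dosage, but the hypotheses and SAP ignore session count: retention results pool two regimens, and the dosage contrast has no analysis

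*Combined protocol and SAP*

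**What the plan says.** Section 6 (Research Plan), Study Overview, says of qualifying participants: "They will attend either one or two intervention sessions (randomly determined to study dosage effects". Under Walking practice protocol it adds: "For most participants, the walking practice protocol will be completed in a single visit". It then says that "a subset of participants (up to 20) will perform the walking practice protocol twice so that we can study dosage effects", and on selection: "This subset will be selected randomly". Selection within the four groups is not mentioned. The intervention sample is capped at forty.

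Retention timing appears twice. Study Overview has "2 days following the study intervention visit, participants will return to perform the" practice task; the Follow Up Visit section has "Approximately 2 days after the intervention visit, participants will return to the lab". Both refer to a single intervention visit.

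Section 5 (Specific Aims) orders the four stimulation-by-insole groups within session (Hypothesis 1a) and carries that ordering to retention: "At the 2-day retention test, effect sizes will support the same findings described for Hyp 1a". The Statistical Analysis Plan begins "Effect sizes for between-group differences will be calculated for" gains in walking speed and makes a parallel comparison at retention. It gives the purpose as effect sizes and variances for sizing a later, larger trial, and it disclaims power for group tests. Neither the hypotheses nor the Statistical Analysis Plan mentions the number of sessions.

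**The concern.** Session count is a randomised factor, introduced for a stated reason, that then drops out of the plan. Three things follow.

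- At retention, each arm's mean and SD average over an unspecified mix of one- and two-session people. Any difference between the regimens goes into the SD.
- The dosage contrast is named in section 6 but has no estimate, interval or model.
- Because selection ignores arm, the arms can differ by chance in how many people practised twice.

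Two definitions are also left open for two-session participants: which session supplies the Hypothesis 1a measurement, and which session starts the 2-day retention interval.

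This matters because the effect sizes and variances are the study's main product. A second sham session adds practice but only seconds of current, so a session effect that differs between active and sham is conceivable. The documents do not establish one.

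**Working it through.** The plan states no power, alpha, SD or session effect, so it has no figure of its own to reproduce.

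**Inputs from the documents.** Up to 40 participants, four groups, up to 20 with two sessions.

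**Assumptions.** Equal allocation, so 40/4 = 10 per arm (no ratio is stated). Session effect *g* = 0.5 within-stratum SD, range 0.3 to 0.8. Fraction with two sessions *f* = 0.25 (10 of 40) or 0.5 (20 of 40, the cap). The lower value is shown because a single visit for most participants does not fit exactly half having two.

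**1. Session effect equal in all arms.** Pooled variance is 1 + f(1−f)g². A true d of 0.50 reads 0.50/√(1 + f(1−f)g²). Planning n is per group, two-sided 5%, 80% power; it is 64 at d = 0.50.

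| f | g | variance inflation | d reads | planning n |
|---|---|---|---|---|
| 0.25 | 0.3 | 1.7% | 0.496 | 65 |
| 0.25 | 0.5 | 4.7% | 0.489 | 67 |
| 0.25 | 0.8 | 12.0% | 0.472 | 72 |
| 0.5 | 0.3 | 2.3% | 0.494 | 66 |
| 0.5 | 0.5 | 6.3% | 0.485 | 68 |
| 0.5 | 0.8 | 16.0% | 0.464 | 74 |

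**2. Selection that ignores arm.** By the exact hypergeometric distribution, two given arms of 10 differ by at least 3 two-session people with probability 0.20 (10 of 40) or 0.27 (20 of 40). At g = 0.5 the resulting shift in a pairwise contrast has mean 0 and SD 0.098 or 0.113. The variance of a 10 v 10 contrast is 2/10 = 0.20, so the added variance is 0.098²/0.20 = 4.8% or 0.113²/0.20 = 6.4%. Selecting within arms in equal numbers removes it.

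**3. Extreme case: extra gain only with active stimulation.** The pooled active-versus-sham contrast exceeds the one-session effect by f × g:

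- 10 of 40: 0.075, 0.125 and 0.20 SD at g = 0.3, 0.5 and 0.8;
- 20 of 40: 0.15, 0.25 and 0.40 SD.

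The standard error across insoles (20 v 20) is √(2/20) = 0.32 SD. Only the 0.40 exceeds it.

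**4. Should planning values come only from the one-session stratum?** Compare root-mean-square error for the one-session effect in this same extreme case. Pooled across insoles it is √((fg)² + 0.1(1 + f(1−f)g²/2)). In the stratum it is √(2/15) = 0.365 (15 v 15) or √(2/10) = 0.447 (10 v 10).

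| | g = 0.3 | g = 0.5 | g = 0.8 | stratum |
|---|---|---|---|---|
| 10 of 40, pooled | 0.326 | 0.343 | 0.382 | 0.365 |
| 20 of 40, pooled | 0.352 | 0.407 | 0.518 | 0.447 |

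Pooling is more accurate at 0.3 and 0.5 and less accurate at 0.8. For a pairwise contrast at one insole type, pooling is better in all six settings: 0.455, 0.469 and 0.502 against 0.516 at 10 of 40; 0.474, 0.518 and 0.613 against 0.632 at the cap.

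**5. Precision of a dosage estimate.** Four arm means and one session term leave 40 − 5 = 35 degrees of freedom, t = 2.03. The 95% half-width is 2.03 × √(1/20 + 1/20) = 0.64 SD at 20 v 20, or 2.03 × √(1/10 + 1/30) = 0.74 SD at 10 v 30.

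**The case against.** The case against giving this much weight is substantial. The study is a pilot with a one-paragraph analysis plan, dosage is not among its aims, and the planning n moves by only a few per group. The Statistical Analysis Plan fixes no model, so pooling is the literal reading and not a stated rule. All of that stands and limits the size of the point. It does not supply the missing analysis.

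Four stronger readings are tempting, and the documents do not support them.

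- *The planning value is lost.* Session count is assigned by design, and nothing prevents tabulating by it.
- *The later trial would be underpowered.* In the extreme case, at 10 of 40 and g = 0.5, a one-session d of 0.50 reads (0.50 + 0.125)/√1.023 = 0.62. A trial sized on that (43 per group) would have 63% power for the one-session effect. This needs an assumed session effect, confined to active stimulation, and a planner who ignores session count. The documents establish none of these.
- *The retention passages contradict each other.* They do not. Both use a loose singular, and measuring after the last session is a natural reading. The wording needs clarifying.
- *No dosage comparison is intended.* Section 6 names the contrast and its purpose. What is missing is its analysis.

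The objection also defeats one possible remedy. Taking planning effect sizes only from session-count strata would usually make them less accurate at this sample size.

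**Conclusion.** The omission is certain: a randomised session factor has no place in the hypotheses or the Statistical Analysis Plan, and its subset is not selected within arms. Random selection keeps the arm contrasts unbiased in expectation.

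The numerical effect is modest. With an equal session effect of 0.5 SD, pooled variance is about 5% to 6% too high, and unstratified selection adds a similar 5% to 6% to contrast variance. A session effect confined to active stimulation would shift the pooled contrast by less than its standard error, except towards the top of the range at the cap. These sizes rest on the assumed session effect, equal allocation and full enrolment; the omission does not. It is worth correcting because the correction is nearly free.

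**What to change.** - Select the two-session subset within each arm, in numbers as equal as possible.
- Use session 1, which everyone has, for Hypothesis 1a.
- Keep the pooled four-group retention contrasts, but take the SD from a model that includes session count. With balanced arms this term leaves the contrasts unchanged and only cleans the SD. If the session effect differs by arm it does so in part, so the descriptive table below is still needed.
- Report the number of two-session participants per arm, and descriptive retention means and SDs by arm and session count.
- Report the one- versus two-session difference with its 95% confidence interval, labelled exploratory.
- Clarify in Study Overview and Follow Up Visit which session starts the 2-day interval for two-session participants. The choice is the investigators'.
- Do not require planning effect sizes to come only from session-count strata.

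The cost is a stratified selection list, a few sentences in the Statistical Analysis Plan and one degree of freedom. The dosage interval will be wide. If enrolment is complete, the within-arm selection can no longer be made, but the reporting changes still apply.

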During the walking practice protocol, participants will receive either active or sham transcutaneous spinal direct current stimulation (tsDCS) and will wear either smooth or textures shoes insoles. Specifically, participants will be randomized to one of four groups: active tsDCS with smooth insoles (*active/smooth group*); 2) sham tsDCS with smooth insoles (*sham/smooth group*); 3) active tsDCS with textured insoles (*active/textured group*); and 4) sham tsDCS with textured insole (*sham/textured group*). More detail about tsDCS and insoles are given below.

Transcutaneous spinal direct current stimulation (tsDCS) during walking practice protocol
tsDCS will be delivered to the posterior lumbar region of the spinal cord during walking using a commercially available direct current stimulation unit (Soterix Medical Inc). Each tsDCS electrode is comprised of a carbon rubber electrode encased in a saline-soaked sponge. The anode electrode will be placed on the skin over the 11th and 12th thoracic vertebrae, and the cathode electrode will be placed over the umbilicus. This electrode configuration has been shown to appropriately target the lumbosacral spinal cord, as validated by modeling of electrical current flow⁴² and by gains in lower extremity motor performance.²⁵ A standard dosage of up to 30 continuous minutes of 2.5 mA stimulus will be used. This dosage (or similar) has been used in numerous prior studies and has been shown to be well-tolerated and to produce measurable changes in reflex activity and/or lower extremity motor performance.^{23-25,38,39,43,44} An identical electrode arrangement will be used for the sham condition, except the stimulation will be delivered in a brief ramp-like manner for just a few seconds at the beginning and end of the stimulation period. This sham approach is widely used in the field of direct current stimulation, and has been reported to be indistinguishable from active stimulation.^{39,45} This is because participants quickly habituate to the sensation of active stimulation.

Textured Shoe Insoles during walking practice protocol

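### Session number (one or two) is drawn at random with no stated link to arm and is absent from the arm comparison, so chance imbalance can add avoidable error to the retention effect sizes

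*Combined protocol and SAP*

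**What the plan says.** Section 6 (Research Plan), Study Overview, sets the size: "Up to forty older men and women will be enrolled in the intervention component of this study". On the number of sessions it says: "They will attend either one or two intervention sessions (randomly determined to study dosage effects".

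The walking practice protocol, under Walking Practice Visit(s), has two sentences that bear on the split. The first is "For most participants, the walking practice protocol will be completed in a single visit". The second is that "a subset of participants (up to 20) will perform the walking practice protocol twice so that we can study dosage effects". How that subset is chosen is given in one line: "This subset will be selected randomly".

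The next paragraph describes arm assignment on its own: "Specifically, participants will be randomized to one of four groups". Neither draw has a stated allocation ratio, block size, stratification factor or combined arm-by-session layout.

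Hypothesis 1b (Specific Aims) orders the four arms on the 2-day retention test. The Statistical Analysis Plan paragraph near the end of the protocol calculates between-group effect sizes for that test. It names no factor, stratum or exclusion for session number and gives no dosage analysis. It disclaims power and says the aim is effect sizes and response variance for planning a larger trial.

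**The concern.** A participant with two sessions repeats the practice, with the assigned stimulation and insole, before retention is measured. The protocol treats this as something that may matter, because the subset exists to study dosage. If one arm happens to contain more two-session participants than another, part of the difference in their retention means comes from amount of practice and not from tsDCS or insole.

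With about 10 people per arm, a simple draw often leaves the arms unequal. The effect sizes are the intended product of this study and will feed a later sample-size calculation, so error that can be removed for nothing is worth removing. The dosage question is affected as well, because it depends on how many people fall in each arm-by-session cell.

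**Working it through.** The plan gives no sample-size, power or imbalance figure, so there is nothing of its own to reproduce.

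**Inputs**
- From the documents: N up to 40; four arms; two-session subset K up to 20.
- Assumed: 10 per arm (no ratio is stated); K = 20 unless noted; the draw ignores arm.
- Assumed: a second session changes retention by g = 0.2, 0.5 or 1.0 SD. The documents give no value.

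**Step 1: how unequal the arms become.** If K of 40 are drawn without regard to arm, the counts (x1, x2, x3, x4) follow the multivariate hypergeometric distribution:

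P = C(10,x1)·C(10,x2)·C(10,x3)·C(10,x4) / C(40,K).

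All arms equal at K = 20: C(10,5)^4 / C(40,20) = 252^4 / 137,846,528,820 = 0.029.

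Summing exactly over all possible counts:

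| K | All arms equal | Highest minus lowest ≥ 3 | Highest minus lowest ≥ 4 | A given pair differs by ≥ 3 |
|---|---|---|---|---|
| 20 | 2.9% | 64% | 41% | 27% |
| 16 | 3.1% | 63% | 39% | 26% |
| 12 | 3.7% | 57% | 33% | 23% |
| 8 | 5.3% | 46% | 21% | 17% |

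**Step 2: size of a typical imbalance.** For two arms, the SD of the difference in two-session share is sqrt(2·S²/10), with S² = K(40−K)/(40·39). At K = 20, S² = 400/1560 = 0.256, so the SD is sqrt(0.0513) = 0.226, or 22.6 percentage points. Its mean is zero.

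**Step 3: effect on a retention contrast.** Shift = g × difference in share.

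| Assumed g (SD) | Shift at a 1-SD imbalance (0.226) | Shift at a 3-of-10 gap (0.30) |
|---|---|---|
| 0.2 | 0.05 SD | 0.06 SD |
| 0.5 | 0.11 SD | 0.15 SD |
| 1.0 | 0.23 SD | 0.30 SD |

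**Step 4: comparison with sampling error.** The standard error of a standardised difference with 10 per arm is sqrt(2/10) = 0.447 SD. Adding the imbalance, with no adjustment, gives sqrt(0.2 + g²·0.0513):
- g = 0.2: 0.450
- g = 0.5: 0.461
- g = 1.0: 0.501

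**Step 5: cells for the dosage question.** At K = 20 a balanced draw puts 5 in each of the eight cells. Under the simple draw, the smallest cell has 3 or fewer in 64% of draws, 2 or fewer in 21%, and one or none in 3%.

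**Step 6: after the change.** Drawing within arm makes the share difference zero, so the shift is zero and the standard error returns to 0.447. Balance alone does not remove the spread from mixing two session counts in one arm. At a half-and-half split, the within-arm SD is inflated by sqrt(1 + g²/4): 1.03 for g = 0.5 and 1.12 for g = 1.0. Only a session term in the analysis removes that.

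**The case against.** The strongest reply has five parts.

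- **Silence is not a procedure.** A reader might infer that the protocol specifies a draw unrelated to arm. It does not: random selection is compatible with selection inside each arm. This stands, so the finding is that the link is unstated. Still, staff could follow the text exactly and use an unrestricted draw.
- **It is not bias.** A reader might infer that the design favours an arm. A random draw favours none, and the imbalance averages zero over repeated randomisations. This stands. What remains is added error in the one allocation that is realised.
- **The 64% is a worst-pair figure.** It compares the highest with the lowest of four arms. For a given contrast, 27% is the relevant figure. At g = 0.5, the overall standard error rises only from 0.447 to 0.461, about 3%. This stands, and it limits how much weight the point can carry in a pilot that disclaims power.
- **Nearly empty cells.** A reader might fear that cells will be too thin to rescue by adjustment. At K = 20 that is rare (one or none in 3% of draws). At K = 12 it is 43%, but perfect balance would then give only 3 two-session participants per arm, so the subset size is the main cause.
- **Analysis can repair most of it.** A session factor would largely remove the shift. This is correct, but the Statistical Analysis Plan has no such factor, and adjustment does not even out the cells. The two changes complement each other.

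It is also tempting to say that two sessions double practice and stimulation. The documents do not support that: a session is 10 to 20 passes, so two short sessions can equal one long one, and the sham arms receive only brief ramps.

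**Conclusion.** The point holds as an inexpensive improvement to allocation and analysis, not as a flaw that invalidates the comparison. If the two-session subset is drawn without regard to arm, unequal numbers are almost certain (97% of draws at 10 per arm and 20 drawn), and the pattern is similar for smaller subsets. The effect on a retention contrast is modest to moderate: 0.06 to 0.30 SD at a 3-of-10 gap over the assumed session effects, always below the sampling error of about 0.45 SD.

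The conclusion rests on equal arms of 10, on a draw that ignores arm, and on a second session having some effect on retention. The documents settle none of these. It matters mainly because the effect sizes are what the study is meant to deliver and the planned comparison does nothing to take session number out of them.

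**What to change.** **Protocol, walking practice protocol.** Replace the sentence "This subset will be selected randomly" with a statement that session number is randomised within each of the four arms, in blocks, at the planned proportion of one-session to two-session participants. Blocking keeps the arms close to balanced if fewer than 40 are recruited.

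**State the proportion.** Five of 10 per arm applies only if the full 20 are intended. That would be half of 40, which does not fit "For most participants, the walking practice protocol will be completed in a single visit". The two statements must be reconciled by the investigators. For the same reason, eight equal arm-by-session cells should not be imposed by default: they would fix the split at one half and could add visits.

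**Statistical Analysis Plan.** Include session number as a factor in the 2-day retention comparison, so that the reported effect sizes and variance do not absorb differences in amount of practice.

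**Cost.** One sentence in each place and a revised allocation list. No visits or participants are added.
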